D2C is a structural intervention designed to sustainably change the HIV care providers' practices and facilitate information exchange at the facility level. To address the implementation science questions by measuring the provider-level outcomes and avoid contamination of the control condition due to unblinded allocation of intervention at the patient level, we propose a cluster-randomized trial design for this pilot study and the prospective RCT. We will select eligible HIV clinics (see "Study Sites," above) and randomly assign them 1:1 either to the intervention or the control arms. To achieve greater comparability between the arms, we will match pairs of eligible sites based on organizational context factors derived from Aim 1 data analysis, including facility size and type (e.g., NGO vs. public clinic), service delivery structure (e.g., social workers vs. nurses), and existing services for HIV-positive PWID (e.g. Steps Toward Health) and will randomize within the pairs. This will minimize the degree of between-cluster variation within the groups and increase power and precision.

Randomization will be conducted by the data manager using a computer program.

Sample size

We used methodology from Hayes et al⁸⁴ to determine the effect size that the intervention needs to demonstrate in a feasible matched-pair randomized trial. We assumed the cluster size of 75 patients (based on the optimal case manager workload) with 5 clusters per arm (potentially manageable number given the existing research infrastructure in Ukraine), coefficient of variation between clusters within matched pairs equal to 0.15 (empirically estimated based on the data from 56 clinics in the ART OPTI study, see Previous Studies), power of 80% and 0.05 significance level. Proportion of participants re-engaging into ART within 3 months after inclusion into the study was used as the key outcome. Under the assumptions, the relative difference between the study arms should be at least 22% (e.g. 50% vs 72%). The adjacent chart shows the power and sample size of a pilot trial needed to detect this difference with 0.05 significance level. To achieve 80% power, we will need to recruit 160 participants, or 80 per arm. We propose to divide the sample equally between 4 sites (2 per arm) to test the matching procedures. We do not adjust for loss-to-follow-up because for our main outcomes (ART initiation, viral suppression), loss to follow-up is equal to not achieving the outcome.

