Intervention Overview

Clinics randomized to the intervention arm will implement the D2C strategy as described above, including Health Data Information, Active Surveillance, and Case Management with the addition of the data component. The D2C strategy will involve a 5-step process: (1) identify not-in-care PLWH using the MIS, (2) verify eligibility criteria, (3) contact patients and invite to visit the clinic, (4) determine care status and reengage into care, and (5) provide case management services and confirm engagement in care.¹²

D2C Ukraine

Steps 1 and 2 will follow the same procedure at both intervention and control sites to ensure equal conditions of study enrollment. Step 3 will be conducted using Active Outreach at the intervention sites. Steps 4 and 5 will be achieved through use of an Acuity Tool and derived Acuity Score. The Acuity Tool will be used to identify barriers to HIV care engagement, including mental health and substance abuse, and to establish referrals to other services, as described above in Overview of Data to Care Strategies.

Procedures

Patient selection and verification of inclusion criteria

A Recruiter (clinical staff authorized to access MIS at each site) will use the D2C module in the MIS to access the “Tracking Journal” which includes patients who have a confirmed HIV diagnosis, started ART, and missed their clinical appointments (medication pick-up or other). Going through the list ('New cases' or 'In progress' or 'Not tracked' sections), Recruiter reviews the MIS data (including in other modules) and identify patients who meet the following criteria:

- a) registered within the MIS as having received a positive HIV diagnosis at any time in the past
- b) missed a clinical visit (ART pick-up or other) more than 7 days ago
- c) registered with IDU as probable mode of HIV transmission, or history of IDU documented at any clinical visit
- d) not been contacted by other clinical staff after the current missed visit
- e) 18 years or older

For each patient meeting these criteria, Recruiter puts an “E” letter in the beginning of the Comment field in the Tracking Result section (before any other text in this field, separated by a space). This letter indicates that the patient is eligible for recruitment into the study and filters the Tracking Journal to display only these patients.

Patient outreach and verification of exclusion criteria

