- use Acuity Tool to assess patient-identified financial, socioeconomic, and housing profiles and provide comprehensive internal or external referrals for supplemental or long-term resources;
- develop and implement personalized treatment plans for all clients based on the acuity assessments through existing case management programs;
- ensure accurate tracking and documentation of all interactions and activities with patients using the acuity tool and Tracking Module within the MIS;
- establish, develop, and maintain professional relationships with diverse treatment and service providers, including AIDS care, primary care, substance use, mental health, and social services;
- maintain current contact information using the Contact Information Form (Annex 0) and updates it at each visit.

Additionally, Case Managers assist Interviewers to schedule follow-up interviews (see below) in conjunction with the Intervention sessions (at 6 and 12 months).

Control Condition

Clinics randomized to the standard of care arm will continue to implement their client identification processes and case management as usual. One of the most common interventions with a focus on PWID is Steps Toward Health,⁸⁵ a case management program developed and tested through the PEPFAR-funded RESPOND project.^{8,86} It is theory-driven and standardized in manuals that contain background information, logic models, client assessment worksheets, step-by-step instructions for each session, and monitoring and evaluation guidelines. This 5-session intervention includes modules on self-care, HIV transmission risk reduction, drug treatment, and ART adherence. It does not include active outreach, client tracking, or tailored treatment components. Other possible interventions include Community-based Retention Intervention, Patients' School, and others.

Provision of these interventions (the fact of enrollment) will be recorded in the MIS by Recruiter, but the actual process data will not be collected.

Data Collection

Data on **primary outcomes** will be obtained from clinical records in the MIS and absence of data will be equal to not achieving the outcome, therefore the effective sample size will be exactly 160 patients. Data from the MIS will be extracted monthly (Annex 6). The primary outcomes are defined as:

- Engagement in HIV care: at least 3 clinical visits over at least 6 months within 12 months after study enrollment.

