We have powered this pilot study to evaluate feasibility of a prospective cluster RCT. The RCT will be considered feasible if the difference in the proportion of patients achieving the primary outcome (engagement in HIV care) will reach 22% between the study arms. We will estimate the impact of the intervention on the HIV care continuum using mixed effects models. For all outcomes, the data will have the same structure, with observations (t) nested within participants (i) nested within sites (j) nested within matched pairs (k). The correlations among observations will be addressed by using fixed-effects indicators for matched pair and normally distributed random intercepts for sites and for participants. Our mixed-effects models will include indicators for each of the two follow-up assessments, an indicator for site group assignment, and two group-assignment-by-follow-up interaction terms. We will also include sex/gender, age, and baseline covariates that have been identified in preliminary analyses as varying significantly across sites. A logit link function will be used for the primary outcome of ART (re-)initiation (defined above), and the coefficients for the two group-assignment-by-follow-up interaction terms will provide the estimates of the subject-specific intervention effects at 6 and 12 months post-baseline. We will examine the effects of sex/gender, age, substance use severity, ART history at baseline and other covariates in the multivariable models.

We will characterize patterns of behavior that impact HIV transmission (episodes of syringe sharing and episodes of unprotected intercourse in the prior 30 days without viral suppression) and we will use the same mixed-effects approach described above but with a log link function and negative

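### The 22-point feasibility threshold was derived for 3-month ART re-engagement but is applied to 12-month engagement in HIV care, so outcome and threshold must be reconciled

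*Combined protocol and SAP*

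**What the plan says.** Three places in the combined protocol and SAP matter.

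- **Specific Aim 2, Sample size.** The future matched-pair RCT is assumed to have 5 clusters per arm, 75 patients per cluster, 80% power, a 0.05 level and a CV within pairs of 0.15, "empirically estimated based on the data from 56 clinics in the ART OPTI study". The outcome is explicit: "Proportion of participants re-engaging into ART within 3 months after inclusion into the study was used as the key outcome". The result is that "the relative difference between the study arms should be at least 22% (e.g. 50% vs 72" per cent). The pilot is then sized to detect that difference at the 0.05 level: "To achieve 80% power, we will need to recruit 160 participants, or 80 per arm", split over 4 sites.
- **Data Collection, primary outcomes.** Engagement is its own entry: "Engagement in HIV care: at least 3 clinical visits over at least 6 months within 12 months after study enrollment". ART (re-)initiation is a separate entry with a 3-month window.
- **Statistical Analysis and Feasibility Assessment.** The section opens "We have powered this pilot study to evaluate feasibility of a prospective cluster RCT" and then gives the rule: "The RCT will be considered feasible if the difference in the proportion of patients achieving the primary outcome (engagement in HIV care) will reach 22" per cent. It attaches no test or interval to the rule. Later in the same section, ART (re-)initiation is the outcome called primary.

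**The concern.** A detectable difference belongs to one outcome, because it depends on that outcome's control rate and between-cluster variation. Here it was worked out for a 3-month ART outcome and then used as the pass mark for a 12-month visit outcome with neither input stated.

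At stake is the feasibility verdict on the RCT, for which I found no other numerical criterion. If engagement is really meant, 22 points could be stricter or more lenient than the difference the planned RCT could detect. If it is not meant, the protocol names the wrong outcome in its decision rule. The wording adds a smaller ambiguity: the Sample size section calls the difference relative, and the rule says only 22 per cent.

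**Working it through.** **Step 1: the two uses of 22.**

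| | Where 22 is derived | Where 22 is applied |
|---|---|---|
| Section | Sample size | Statistical Analysis and Feasibility Assessment |
| Outcome | Return to ART | Engagement in HIV care |
| Window | 3 months | 12 months |
| Control rate | 50% (example) | Not given |
| CV | 0.15 | Not given |

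**Step 2: absolute or relative.** 72 − 50 = 22 percentage points; 22/50 = 44% relative. The figure is absolute.

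**Step 3: reproduce the 22.** The plan cites the Hayes–Bennett method. Clusters per arm are

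c = a + (z_α + z_β)² × [p0(1−p0)/m + p1(1−p1)/m + k²(p0² + p1²)] / (p1 − p0)²,

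with a = 1 unmatched and a = 2 matched. From the Sample size section, p0 = 0.50, p1 = 0.72, m = 75, k = 0.15.

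- Bracket: 0.25/75 + 0.2016/75 + 0.0225 × (0.25 + 0.5184) = 0.00333 + 0.00269 + 0.01729 = 0.02331.
- Divided by 0.22² = 0.0484: 0.4816.
- Two-sided, (1.960 + 0.842)² = 7.849: 3.78, so c = 4.78 unmatched or 5.78 matched.
- One-sided, (1.645 + 0.842)² = 6.183: 2.98, so c = 4.98 matched.

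Five clusters per arm therefore fit 50% vs 72% in the unmatched two-sided or the matched one-sided version. The plan does not state sidedness. The matched two-sided version needs more than 5 clusters and would detect 25.1 points.

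**Step 4: change the inputs.** I solved the same formula for p1 − p0 at c = 5 with k = 0.15. The control rates are assumptions. Results are in percentage points:

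| Control rate | 30% | 40% | 50% | 60% |
|---|---|---|---|---|
| Unmatched, two-sided | 15.9 | 18.7 | 21.3 | 23.8 |
| Matched, one-sided | 16.4 | 19.2 | 21.9 | 24.5 |
| Matched, two-sided | 18.8 | 22.1 | 25.1 | 28.1 |

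With k also varied over an assumed 0.10 to 0.20, the three versions together run from 13.2 points (unmatched two-sided, control 30%, k = 0.10) to 38.5 (matched two-sided, control 60%, k = 0.20).

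**Step 5: secondary note on the 80%.** I read the rule as a cut-off on the observed difference.

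- *Chance of meeting the rule.* With 80 per arm and true rates of 50% and 72%, the exact binomial probability of an observed difference of at least 22 points is 50.9%. Simulation with 2 sites of 40 per arm and CV 0.15 gives about 51%.
- *Significance test, ignoring clustering.* The null standard error is √(2 × 0.61 × 0.39/80) = 0.0771 and the alternative standard error is √(0.4516/80) = 0.0751. Power is Φ[(0.22 − 1.96 × 0.0771)/0.0751] = 82%, close to the plan's 80%.
- *Significance test with clustering.* For 2 sites of 40 per arm at CV 0.15, the standard error is √[(0.4516/40 + 0.01729)/2] = 0.1195. Power is Φ(0.22/0.1195 − 1.96) = Φ(−0.12), about 45%.

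**The case against.** The best defence is that the parenthesis naming engagement is only a loose label. The Sample size section lists ART initiation and viral suppression as the main outcomes, and the analysis section later calls ART (re-)initiation primary. If so, the repair is one phrase and the table in Step 4 is moot. This stands as a possibility, and it decides which fix is cheaper. It does not remove the contradiction, since engagement is separately defined with a different window.

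It can also be said that this is a pilot. Its Study Design section has it measure the effect size and CV, its findings will size the RCT, and feasibility is also judged from usage and qualitative data under Aim 3. That stands too. It limits the point to the feasibility verdict and leaves the eventual RCT sample size untouched.

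A reader might go further and infer that the pilot is defective because its rule succeeds only half the time at the planned effect. The documents do not support that. Any cut-off on a roughly unbiased estimate is reached about half the time when the truth equals the cut-off. The plan never attaches 80% to the rule, and a strict rule may be intended.

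**Conclusion.** The mismatch is real and rests on the text alone: the threshold was derived for one primary outcome and is applied to another. It should be fixed, at modest cost.

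Its size depends on what engagement would look like. Under the plan's own RCT design and CV 0.15, the detectable difference lies between 15.9 and 28.1 points for control rates of 30% to 60%, and between about 13 and 38 if the CV is 0.10 to 0.20. These control rates and the CV range are my assumptions.

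Two stronger conclusions might be drawn, and neither is supported. First, the 22 is not shown to be wrong for 3-month ART: two versions of the cited formula reproduce it closely. Second, it cannot be said that no planning basis for engagement exists anywhere. The previous-studies material cited for the CV and the sample-size chart were not in the text I could read. I can say only that the available text gives no control rate or CV for engagement.

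**What to change.** Make outcome and threshold agree between the Sample size section and Statistical Analysis and Feasibility Assessment, in one of two ways.

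1. **Apply the 22-point rule to 3-month ART (re-)initiation**, the outcome it was derived for. First check that a 50% control rate is plausible. Candidates come from a list of "patients who have a confirmed HIV diagnosis, started ART, and missed their clinical appointments", and they consent only after returning to the clinic. Above a 78% control rate a true 22-point gain is impossible (100 − 22 = 78). No rate for this population is given, so this is a check and not a claim. The cost is a wording change, and the rule would no longer speak to 12-month engagement.
2. **Keep engagement and re-derive the threshold** from a stated control rate and CV, with sidedness and matching stated. The medical information system records visits kept, so both inputs could be estimated from it, subject to the same selection on return to clinic. The cost is one data extract, and the threshold may move away from 22.

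Under either option:

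- In the Sample size section, replace relative with absolute (22 percentage points).
- In the feasibility rule, say that 22% means percentage points, and report the observed difference with a cluster-adjusted confidence interval.
- If the 80% is restated, say that it describes a significance test ignoring clustering. It is not the chance of meeting the rule.

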binomial distribution. These analyses will provide parameters for estimating the rate of onward HIV transmission for the cost-threshold analysis. All analyses will include the use of the mixed effects "meqrlogit," "meologit," and "menbreg" procedures using Huber/White robust variance-covariance estimators. We will examine whether missingness is associated with observed data using standard methods.^{98–100} We will conduct a second set of outcome analyses using multiple imputation to evaluate the robustness of the primary outcome analyses to missingness and report estimates based on multiple imputation that would be valid based on the assumption that the data are missing at random (MAR). We will produce imputed datasets ($m > 10$) using chained equations,¹⁰¹ run outcome analyses on all sets, and derive point and standard error estimates for treatment effects and other parameters from the distribution of estimates from the outcome analyses with imputed datasets.

We will also evaluate the use of mixed proportional odds regression^{102,103} for determining whether intervention exposure is associated with an individual's location on five distinct stages of HIV care continuum: (1) not engaged in HIV care in the prior six months; (2) engaged in HIV care in the prior six months but no ART use in the prior 30 days; (3) ART use in the prior 30 days but no evidence of viral suppression in the prior 6 months; and (4) ART use in the prior 30 days with evidence of viral suppression in the prior 6 months. The HIV care continuum can be viewed as an ordinal categorical variable, and ordinal logistic regression will be used to evaluate if group assignment is associated with the location along the HIV care continuum. We will use the Score test to evaluate whether the proportional odds assumption of ordinal logistic regression.¹⁰⁴

These analyses will be essential for planning a full study. The findings will be used for sample size estimates, and data on HIV transmission risk will be used to determine whether the intervention could reasonably be cost-saving or cost-effective. This pilot analysis will provide important information on the feasibility of using ordinal logistic regression in a larger trial or in other analyses of the HIV care continuum.

Specific Aim 3a: To assess the feasibility, acceptability, and implementation-related processes and outcomes of the D2C strategy

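### For repeatedly measured outcomes, the group-by-follow-up effects omit clinic differences in change from their standard errors, and the stated robust errors do not repair this with four clinics

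*Combined protocol and SAP*

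**What the plan says.** All of this is in Specific Aim 2 of the combined protocol and SAP.

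- **Model (Statistical Analysis and Feasibility Assessment).** One structure is meant to serve every outcome: "For all outcomes, the data will have the same structure". Correlation is handled by "fixed-effects indicators for matched pair and normally distributed random intercepts for sites and for participants". No site-by-follow-up term or random site slope appears anywhere.
- **Effect (same section).** "Our mixed-effects models will include indicators for each of the two follow-up assessments", together with a group indicator and two interactions, and "the coefficients for the two group-assignment-by-follow-up interaction terms will provide the estimates of the subject-specific intervention effects at 6 and 12 months post-baseline".
- **Standard errors (same section).** All analyses use Stata mixed-model "procedures using Huber/White robust variance-covariance estimators". The level of clustering, any small-sample correction and the reference distribution are not stated.
- **Clusters (Study Design and Sample size).** The plan will select clinics and "randomly assign them 1:1 either to the intervention or the control arms", within matched pairs. "We propose to divide the sample equally between 4 sites (2 per arm) to test the matching procedures", which is 40 participants per site.
- **Clinic variation (Sample size).** The plan assumes a "coefficient of variation between clusters within matched pairs equal to 0.15", estimated from 56 clinics. It is used for ART re-engagement within 3 months, a proportion measured once. No figure is given for how much clinics differ in change over time.
- **Outcomes (Data Collection).** Survey outcomes are collected at baseline, 6 and 12 months. Engagement, ART (re-)initiation and viral suppression are each defined once per participant, over a window after enrolment.

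**The concern.** Each interaction coefficient is a difference between arms in change from baseline. The random site intercept takes the same value at all three assessments, as does the fixed pair indicator, so both subtract out of that change on the linear-predictor scale. What remains in the model's own variance is participant-level noise. If one clinic improves more than another for local reasons, the model counts that as 40 separate participant responses, although only two clinics per arm carry information about it.

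The plan gives reasons to expect clinics to change differently. It randomizes clinics because the intervention acts on provider practice at facility level, and its control condition may be Steps Toward Health or another local programme.

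What is at stake is precision. Intervals for the 6- and 12-month effects would be too narrow, and the plan uses the findings to size a full trial and to inform the cost-threshold analysis.

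**Working it through.** **The plan's own figure.** The plan's only precision figure is 160 participants for 50% against 72%. With 80 independent participants per arm, the exact power of the Pearson chi-squared test is 81.6%, so the figure agrees with a comparison that ignores clinics. It concerns an end-point difference and does not enter the steps below.

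**Inputs.** From the plan: m = 40 participants per site, 2 sites per arm, coefficient of variation 0.15. Assumed: a proportion of 50% at each assessment, a between-clinic SD of change τ = 0.15 × 0.50 = 0.075, and a within-person correlation r from 0 to 0.7. Applying 0.15 to a change is an assumption, because the plan states it for a level.

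**Step 1: closed form.** The variance of one participant's change is v = 2 × 0.25 × (1 − r).

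- Variance with clinic differences in change, for the contrast between arms: 2 × (v/40 + τ²)/2.
- Variance that the planned model uses: 2 × (v/40)/2.
- Ratio: 1 + 40τ²/v, with 40 × 0.075² = 0.225.
- Actual rejection rate of a nominal 5% test: 2 × P(Z > 1.96/SE ratio).

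| r | v | Variance ratio | SE ratio | Rejection rate |
|---|---|---|---|---|
| 0 | 0.50 | 1.45 | 1.20 | 10.4% |
| 0.2 | 0.40 | 1.56 | 1.25 | 11.7% |
| 0.5 | 0.25 | 1.90 | 1.38 | 15.5% |
| 0.7 | 0.15 | 2.50 | 1.58 | 21.5% |

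Smaller clinic differences matter less: at τ = 0.025 the rate is 5.7% (r = 0.2) or 6.2% (r = 0.5).

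**Step 2: simulation of the planned mixed logit with no intervention effect.** There were 4 sites of 40, three assessments, and 1,500 trials per setting.

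- *Site intercepts random, model-based tests.* Participant intercept SD 1 or 2, baseline 20% or 38%, follow-up 50%. Each interaction rejects 3.9 to 4.9% of the time when clinics change alike. It rejects 8.7 to 10.9% when clinic-by-time variation matches a coefficient of variation of 0.15 at follow-up.
- *Site intercepts fixed, four kinds of inference.* Columns give the SD of site change on the logit scale; 0.3 is about the size that 0.15 implies at 50% (0.075/0.25).

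| Inference | SD 0 | SD 0.3 | SD 0.6 |
|---|---|---|---|
| Model-based | 4–6% | 9% | 20–21% |
| Participant-level sandwich | 5–6% | 9% | 20–21% |
| Site-level sandwich, normal reference | 24–26% | 24–25% | 24–25% |
| Site-level sandwich, t with 2 df | 7–8% | 7% | 5–6% |

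In the first simulation, site-clustered errors with a normal reference gave 22 to 26% in all settings.

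**Reading.** Rows 1 and 2 show the missing term: the error rate rises with clinic differences in change. Row 3 shows a different fault: the rate is already about 25% when clinics change alike, because there are only four clusters. Row 4 shows that degrees of freedom based on the sites (4 sites − 2 arms = 2) bring the rate close to nominal.

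**The case against.** The strongest reply is that Huber/White errors are specified for all analyses. If they are clustered on site, the test does not formally assume that clinics change alike, and the random intercepts alone do not decide its null. That stands, and it limits the missing-term argument to model-based or participant-level errors. It does not rescue the plan, because the site-clustered version with a normal reference rejects about a quarter of the time.

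A second reply concerns calibration. The value 0.15 belongs to a once-measured ART outcome, and any single SE ratio depends on the within-person correlation. The ratio of 1.38, for example, holds only at r = 0.5. This also stands, so the result is a range under stated assumptions. No count or ordinal model was simulated.

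A third reply is that this is a pilot. Its feasibility rule is an observed 22% difference in engagement and not an interaction test, and the primary cost model uses point estimates. This is correct and confines the harm to stated precision.

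Two stronger readings are tempting. A reader might infer that clinic differences bias the effect and would be mistaken for an intervention effect on average. Clinics are randomized, so the omission affects precision and does not by itself bias the estimate. A reader might also infer that all primary outcomes are affected. Engagement, ART (re-)initiation and viral suppression have one value per participant, so they have no change from baseline. For ART (re-)initiation, the analysis section nevertheless describes interaction effects at 6 and 12 months, which must first be reconciled with the 3-month definition in Data Collection.

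**Conclusion.** The concern holds for outcomes analysed as change from baseline to 6 and 12 months: care-continuum stage, risk behaviour and quality of life. With model-based or participant-level errors, the standard error omits clinic differences in change. At an assumed SD of change of 0.075 it is too small by a factor of about 1.2 to 1.6 for r between 0 and 0.7. A nominal 5% test then rejects about 10 to 22% of the time in the closed form and about 9 to 11% in the simulations set to the plan's coefficient of variation. With site-clustered errors and a normal reference, the rate is about 22 to 26% for a separate reason, too few clusters. Every normal-reference reading of the section is therefore anti-conservative when clinics differ in change.

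The closed-form sizes rest on the assumed SD of change, a 50% proportion and the assumed correlations. If clinics change alike and errors are model-based or at participant level, the rate stays near 5%.

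**What to change.** In Statistical Analysis and Feasibility Assessment, for the repeatedly measured outcomes:

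1. Allow for site-by-follow-up variation, through a random site-by-follow-up effect or an analysis of site-level changes.
2. Replace normal-reference Huber/White inference with small-sample inference based on the four sites, for example t with 2 degrees of freedom. State the clustering level of any robust variance that is kept. Adding the random effect alone would leave the four-cluster problem in place.
3. Report the 6- and 12-month effects as estimates with intervals and not as significance tests.
4. For binary outcomes, add a sensitivity table over assumed between-clinic variation, for example coefficients of variation from 0 to 0.25, labelled as an assumption. Such a value has no direct meaning for count, ordinal or scale outcomes and should not be fixed in those models.
5. Reconcile the once-per-participant definitions in Data Collection with the repeated-measures model.

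The cost is analysis time and much wider intervals; no new data are needed. The t multiplier with 2 degrees of freedom is 4.30 against 1.96, a factor of 2.2. Combined with SE ratios of 1.20 to 1.58, intervals would be roughly 2.6 to 3.5 times as wide as the model-based ones. That width reflects what two clinics per arm can show about change.

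### Beyond sex/gender and age, covariates enter the effect models because they differ significantly across the four sites, not because they predict outcome

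*Combined protocol and SAP*

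**What the plan says.** The analysis section describes mixed models with "fixed-effects indicators for matched pair and normally distributed random intercepts for sites and for participants". On covariates it says "We will also include sex/gender, age, and baseline covariates", and limits the last group to "baseline covariates that have been identified in preliminary analyses as varying significantly across sites". Sex/gender and age are therefore in the model regardless. Everything else enters on a significance test across sites. No candidate list, test, threshold, cap or timing relative to the outcome data is given.

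The same paragraph later says "We will examine the effects of sex/gender, age, substance use severity, ART history at baseline and other covariates in the multivariable models". It does not say whether those multivariable models are the ones that supply the intervention effect.

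Under Sample size, the design is stated as "We propose to divide the sample equally between 4 sites (2 per arm) to test the matching procedures", with "To achieve 80% power, we will need to recruit 160 participants, or 80 per arm". The baseline survey listed under Data Collection offers a long list of possible candidates: substance use, stigma, mental health, quality of life, risk behaviour, comorbidity and socio-demographics.

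**The concern.** Adjustment improves an analysis when the variable predicts outcome. A test of difference across sites does not ask that question. It passes over a strong predictor that looks balanced, and it admits a variable that differs by site but has no bearing on outcome.

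The four sites also carry the randomised comparison. They give three between-site contrasts, of which one is pair and one is arm, so variables chosen for their between-site difference draw on the little between-site information there is.

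The model is also not known until the data are in hand. Two analysts following the plan could choose different candidates and thresholds and report different effects. The estimates are meant to show the intervention's impact and to feed the sample size of a larger trial.

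**Working it through.** **Inputs from the plan.** 4 sites, 2 per arm, 160 patients (40 per site), 50% against 72%, 80% power, significance level 0.05 (two-sided assumed; the plan does not say).

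**Assumed inputs, not in the plan.** Number of candidates, 5% screening threshold, covariate strength, between-site variation of covariates.

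**1. The plan's sample size.** With p1 = 0.50, p2 = 0.72 and mean 0.61:

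n per arm = [1.96·√(2·0.61·0.39) + 0.8416·√(0.50·0.50 + 0.72·0.28)]² / 0.22² = (1.352 + 0.566)² / 0.0484 ≈ 76, or 152 in all.

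At 80 per arm, the exact power of the uncorrected chi-square test is 81.6%. The stated 160 is thus reproduced on power, as an individually randomised comparison. It contains no covariate term, so the covariate rule does not change it.

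**2. Chance selection.** With k independent candidates that do not truly differ by site, the chance that at least one is flagged is 1 − 0.95^k: 23% for k = 5, 40% for k = 10, 64% for k = 20.

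**3. One covariate, logistic model.** 2,500 simulated trials per scenario; arm, pair and one covariate; Wald test. The arm effect is ln(0.72/0.28) = 0.94 on the log-odds scale, given the covariate. Ranges run over the between-site variation assumed.

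| Covariate log-OR per SD | Power, prespecified | Power, screened | Loss |
|---|---|---|---|
| 0.5 | 79-81% | 77-79% | about 1-2 points |
| 1.0 | 73-77% | 68-69% | 4-8 points |
| 1.5 | 67-68% | 54-61% | 6-14 points |

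- A predictor that does not truly differ by site entered under the screen in only about 4-5% of trials.
- A non-predictor that does differ by site was flagged in 63-98% of trials. Adjusting for it took power from 81-82% to 81% at site SD 0.3 or 0.5, and to 75% at site SD 1.0.
- Type I error under the screen was 3.7-5.6%.
- For a predictor with log-OR 1.0 and site SD 0.3, screen against no adjustment gave type I error 5.6% against 12.5%, power 69% against 63%, and SD of the estimate 0.386 against 0.425.

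**4. Many candidates, linear outcome.** 15 candidates, two of them prognostic and together explaining 24% of outcome variance. The last three columns give the excess variance of the arm effect over a model with the two predictors prespecified. Ranges span repeated runs; the last column is from one run.

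| Baseline ICC | Mean number selected | Both predictors kept | Screen | Screen added to the two predictors | No covariates |
|---|---|---|---|---|---|
| 0 | 0.8 | under 1% | 23-28% | 1-2% | 33% |
| 0.05 | 7.0 | 22% | 39-43% | 18-22% | 89% |
| 0.10 | 10.4 | 47-48% | 50-65% | 37-45% | 155% |

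**5. Many candidates, binary outcome.** With two predictors at log-OR 0.5 each, a logistic model and a standardised risk difference (2,000 trials), power at ICC 0, 0.05 and 0.10 was 73%, 69% and 61% under the screen, against 78%, 78% and 76% prespecified. The losses are 5, 9 and 15 points. Expected non-events are 80·0.50 + 80·0.28 = 62.4, few for 7 to 10 added terms.

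**6. Collinearity bound.** For a patient-level variable in 4 × 40 patients, p < 0.05 in a one-way ANOVA is reached when site explains 4.9% of its variance. At that threshold the variance inflation of the arm term is at most 1/(1 − 0.049) = 1.05.

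**The case against.** The other side has several good points.

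- Sex/gender and age are fixed in advance, and the plan itself names ART history and substance use severity. A reader might infer that the whole adjustment set is chosen by screening; the text does not say that. What stands is that the place of the last two in the effect model is unclear and that all further entry is by the screen.
- A reader might infer that variables differing by site are nearly collinear with arm. For patient-level variables they are not, as step 6 shows. Several added together cost more, but that is a different matter.
- A reader might infer that the screen decides whether the larger trial goes ahead. The feasibility criterion is a 22% difference in proportions engaged in care, with no mention of adjustment, and a logit model does not return that quantity directly.
- The variance figures in step 4 are from a linear model and do not carry over to log-odds. In the logistic simulation, adjustment raised the SD of the log-odds ratio (0.335 to 0.379 at log-OR 1.0 with no site variation); the gain is in power.
- The screen is better than nothing, as steps 3 and 4 show. Imbalance here may also be systematic: the recruitment wording has two arm-specific versions, and intervention-site case managers make extra efforts to reach patients. Removing the rule with no replacement would leave such imbalance untouched.

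These points narrow the concern and shape the fix. They do not defend the screen against prespecified prognostic adjustment, which had higher power in every scenario compared.

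**Conclusion.** The point holds in a limited form. Beyond sex/gender and age, the plan states a selection rule that disregards prognosis and leaves the model to be settled from the data, and a better rule is available at almost no cost. Compared with naming the predictor in advance, the loss is about 1-2 points of power for a weak predictor and 4-8 for a moderate one, and more if many candidates are screened. Those sizes depend on the assumed predictor strength, ICC and number of candidates. The simulations also leave out repeated measures, random intercepts and robust standard errors, and the one-covariate logistic runs had no residual site effect, so they isolate the covariate rule only.

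A reader might also infer a false-positive problem. None was seen when the screen used baseline data alone; the remaining risk is analyst discretion.

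**What to change.** In the analysis section:

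- Remove the across-site significance screen from the primary effect model.
- Prespecify matched pair, sex/gender, age, baseline substance use severity (DAST-10) and one defined baseline ART history variable. That variable must vary in this population: the Tracking Journal used for recruitment lists patients who have already started ART, so ever/never would be nearly constant.
- Report the estimate adjusted for pair only beside it.
- Because recruitment differs by arm, keep adjustment for covariates that differ across sites as a labelled sensitivity analysis, with candidates and threshold listed beforehand.
- State whether the 22% criterion uses the crude or the adjusted difference.

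The cost is wording. DAST-10 is in the baseline survey, and ART history is in the MIS clinical summary. The downside is that an imbalanced predictor outside the list is adjusted for only in the sensitivity analysis.
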